Study protocol

Ultrasound-assisted vs. real-time ultrasound-guided paracentral approach combined lumbar and epidural anesthesia in elderly patients: a randomized controlled study

Version: 2.0

Version Date: 2024/2/1

1. Research background

Traditional body surface marker guided intraspinal anesthesia can meet most of the clinical anesthesia needs, but for the presence of obesity, spinal deformity, senile ligament calcification, previous lumbar surgery history, etc., intraspinal puncture often has technical difficulties. Ultrasound-guided intraspinal puncture can provide anatomical information related to the puncture site, including intervertebral segment, posterior median line of the spine, vertebral canal depth, and distribution characteristics of each ligament, providing a solution for difficult puncture and improving the accuracy and safety of intraspinal puncture 1,2.

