During the implementation of lumbar anesthesia, multiple punctures through ligaments and dura can easily lead to postoperative headache, low back pain, and may increase the incidence of paresthesia and spinal cord hematoma. Ultrasonic-guided spinal anesthesia can reduce the number of passages required to enter the subarachnoid space compared with the traditional signpost guided midline approach. Ultrasound examination before hip and knee replacement provides guidance for intraspinal puncture, which can significantly reduce the number of entry into the subarachnoid space and the number of attempts3. In addition, a pre-ultrasound scan of the spine before puncture can estimate the distance from the skin to the epidural space and determine the appropriate puncture point, which is important in obese women (BMI: 33~86 kg/m²) epidural labor analgesia is especially effective when the epidural needle is placed at the intended puncture point, 76.1% of women did not change the point of re-puncture, 67.4% of women did not redirection4. However, despite the ability of ultrasound to provide anatomical information about the spine, 23 (10.7%) of 218 women in a study had misidentification of 2 or more intervertebral spaces, which increases the risk of intraseptic puncture complications. Subgroup analysis showed that the degree of access to the maternal spinous process had an impact on the recognition of the lumbar space in spinal ultrasound. Women with easy access to the spinous process have a higher success rate of ultrasound-assisted first puncture 5. Based on the posterior longitudinal ligament ultrasonic image scoring system, Weed JT et al. 's study showed that the puncture frequency and puncture time were significantly reduced in the group with a high rating of clear images, suggesting that the calcification level of the posterior longitudinal ligament may be one of the important factors affecting the success rate of ultrasound-guided intra spinal puncture through the posterior median approach.

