This study is intended to include all patients who will undergo combined spinal and epidural anesthesia from October 2023 to October 2024. Adopt PASS V21.0.3 software (2021; NCSS LLC) calculated the study sample size. According to a preliminary study by Chen L et al., the success rate of the first puncture using the USAS technique and the USRTG technique was 80.7% vs 52.6%, respectively. It was calculated that 43 patients were required in each group at a bilateral significance level of 0.05 ($\alpha = 0.05$) and 80% efficacy ($\beta = 0.2$). Taking into account 10% of possible patients dropping out, the sample size was increased to 48 patients per group for a total of 96 patients.

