3.1.3 Exclusion criteria

- 1) Severe obesity ($BMI > 35 \text{ kg/m}^2$);
- 2) Spinal deformity or surgical history;
- 3) Allergic to local anesthetics;
- 4) There are coagulation disorders;
- 5) Communication barriers

4. Research process

1. Preoperative records

Patients were visited according to clinical routine on the day before surgery, and their age, gender, height, weight, ASA grade, and operation name were recorded. Patients were identified according to inclusion and exclusion criteria, informed consent was signed, and basic patient information was recorded.

2. Anesthesia protocol and intraoperative records

Based on a computer-generated table of random numbers, they were randomly assigned to receive combined lumbar and epidural anesthesia in either the US-AS group (n=48) or the US-RTG group (n=48). Patient assignments are hidden by sequentially numbered and sealed opaque envelopes that can only be opened by the attending anesthesiologist when the patient enters the operating room. Patients know nothing about grouping. Neither the intraoperative parameter collector nor the anesthesiologist performing the procedure can blind the groups.

All ultrasound-guided CSEA blocks were performed by an attending anesthesiologist (>100 cases per year) who was skilled in ultrasound-assisted and real-time ultrasound-guided intra spinal block, and another attending physician who was familiar with the procedure was responsible for parameter recording. When the patient enters the room, connect the monitor. Nasal catheter oxygen (oxygen flow 3 L/min) to establish peripheral venous access. 1. Assess the difficulty of palpating the spinous process (1 degree: easy - slight or moderate pressure on the tissue; Grade 2: moderately significant tissue compression; 3 degrees: Difficult/unable to palpate). 2. If the patient could not cooperate due to hip pain, iliofascial space block (20mL, 0.4% ropivacaine) was performed in the supine position, and 15min later, the patient lay on his side (affected side up).

In the US-AS group, the intraspinal structure was evaluated using a portable ultrasonic system (Sonosite, low frequency convex array probe 2-5 MHz) (ultrasonic prescan to determine the best intervertebral space, best puncture Angle and best puncture depth). The measurement methods (in-plane measurement of paracentral transverse section (LTP), out-of-plane measurement of paracentral sagittal section (LSC) and in-plane measurement

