of paracentral sagittal section (IPP)) were recorded, and the optimal puncture section considered by the operator (the widest acoustic window at the back of the complex) was selected to record the best gap, puncture Angle and depth. In the sterile state, traditional blind operation was performed; The positioning time, the depth and width of the retrodural complex, the first successful attempt (first skin piercing without redirection), the number of skin piercings, the number of redirects, and the operation time (probe touching the skin until the end of the operation) were recorded. After successful epidural puncture, 25G lumbar anesthesia needle was inserted (if CSF outflow was not smooth, the epidural needle could be rotated in place and then re-inserted into the epidural puncture). Subarachnoid block (2.5mL/12.5mg of 0.5% ropivacaine without high glucose) was performed immediately after CSF outflow was smooth, followed by epidural catheter. If there is no CSF after withdrawal, skin puncture should be performed again. The maximum number of skin puncture should be 6 times, and the cumulative redirection of each skin puncture should not exceed 6 times. If six skin piercings are unsuccessful, traditional palpation, replacement of puncture Spaces, or general anesthesia are considered and recorded.

In the US-RTG group, the optimal puncture section considered by the operator was selected and recorded directly in the plane of the paracentral transverse section, out of the plane of the paracentral sagittal section or in the plane of the paracentral sagittal section for real-time ultrasound guided lumbar epidural anesthesia. The positioning time, the depth and width of the retrodural complex, the first successful attempt (first skin piercing without redirection), the number of skin piercings, the number of redirects, and the operation time (probe touching the skin until the end of the operation) were recorded. After successful epidural puncture, 25G lumbar anesthesia needle was inserted (if CSF outflow was not smooth, the epidural needle could be rotated in place and then re-inserted into the epidural puncture). Subarachnoid block (2.5mL/12.5mg of 0.5% ropivacaine without high glucose) was performed immediately after CSF outflow was smooth, followed by epidural catheter. If there is no CSF after withdrawal, skin puncture should be performed again.

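### Does leaving the spinous-process palpation grade out of the analysis, with no rule that it be fixed before the envelope is opened, weaken the primary comparison?

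*Protocol*

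**What the plan says.** Section 1 of the protocol reports from an obstetric study that "Women with easy access to the spinous process have a higher success rate of ultrasound-assisted first puncture". It gives no effect size.

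Section 4, item 1 lists what is noted the day before surgery: "their age, gender, height, weight, ASA grade, and operation name were recorded". Eligibility and consent are settled at that visit. Palpability is not on the list, and it is not an inclusion or exclusion criterion.

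Section 4, item 2 says the envelopes "can only be opened by the attending anesthesiologist when the patient enters the operating room". Once the patient is in the room and monitored, the first numbered step is "Assess the difficulty of palpating the spinous process", in three grades. The arm-specific procedures come after it. Each arm then has its own list of recorded items, beginning "The positioning time, the depth and width of the retrodural complex, the first successful attempt", and the grade is not repeated there. On blinding, the protocol says "Neither the intraoperative parameter collector nor the anesthesiologist performing the procedure can blind the groups".

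The primary outcome (section 4, item 3) is success at the first skin piercing with no redirection. The SAP's statistical analysis section, in the part available for this review, compares categorical variables by Pearson chi-square or Fisher's exact test. It names no covariate, stratum or subgroup.

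**The concern.** Three facts together look like a gap. The protocol cites palpability as related to its own endpoint, has staff grade it, and then gives it no analytic use. A prognostic baseline factor left out of the model can cost precision.

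Timing is the second worry. Grading and envelope opening both happen around entry to the operating room, their order is only implied, and neither operator nor recorder is blinded. A grade assigned after the arm is known could be coloured by it. Adjusting for such a grade, or forming subgroups on it, could then introduce bias into a comparison that randomisation had protected.

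If either worry reached the primary result, the trial's main conclusion would be less precise or less trustworthy than it need be.

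**Working it through.** **1. The plan's own sample size.** Inputs from section 3.1.1: 80.7% vs 52.6%, two-sided alpha 0.05, power 80%, 10% dropout. Pooled two-proportion formula, with mean rate (0.807 + 0.526)/2 = 0.6665:

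- Null term: 1.960 × √(2 × 0.6665 × 0.3335) = 1.307
- Alternative term: 0.842 × √(0.807 × 0.193 + 0.526 × 0.474) = 0.536
- n = (1.307 + 0.536)² / 0.281² = 42.99, so 43 per arm
- 43/0.9 = 47.8, so 48 per arm

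Both figures reproduce. The calculation assumes an unadjusted comparison, which is what the SAP plans.

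**2. Validity of the unadjusted test.** Exact binomial enumeration of the Pearson chi-square, at common success rates from 0.50 to 0.807, gives a type I error of 4.7–5.3% at 43 per arm and 5.1–5.2% at 48. Exact power at the planned rates is 81.2% and 85.0%. Leaving out a baseline factor does not bias the randomised risk difference.

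**3. Does the order of grading and opening touch the primary result?** Consent and eligibility are complete the day before, and palpability decides neither. Grading after opening therefore cannot change who is randomised. The grade enters no planned analysis in the available text, so a coloured grade has no route into the primary comparison.

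**4. What would adjustment buy?** The documents give neither the grade mix nor the strength of the association, so both are assumed: mixes of 60/30/10, 50/30/20 and 80/15/5%, and odds ratios (OR) of 1 to 5 per grade. Trials were simulated at 43 per arm with the arm rates held at 80.7% and 52.6%. Each was analysed with a logistic model of arm and linear grade, standardised to a risk difference. The mean unadjusted 95% half-width is 18.8 points. Adjusted half-widths in points, as ranges over the three mixes:

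| OR per grade | Same effect in both arms | Effect in the ultrasound-assisted arm only |
|---|---|---|
| 1 | 19.0 | 19.0 (same case) |
| 2 | 18.4–18.7 | 18.9 |
| 3 | 17.6–18.3 | 18.8 |
| 5 | 16.5–17.7 | 18.6 |

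The right-hand column matters because the cited sentence concerns ultrasound-assisted puncture only. Section 1 also argues that real-time guidance helps with path selection in difficult punctures, which is a reason to expect a weaker palpability effect in that arm. On that reading the adjusted interval is slightly wider at OR 2, unchanged at OR 3, and 18.8 − 18.6 = 0.2 points narrower at OR 5.

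**5. A late start would shrink even that.** The protocol carries "Version Date: 2024/2/1", while enrolment was planned for "combined spinal and epidural anesthesia from October 2023 to October 2024". With even accrual, four of twelve months, about 14 of 43 patients per arm, would precede any new recording rule. Keeping everyone, with those patients as a separate category, gives 18.6–18.8 at a common OR of 2: a gain of 0.0 to 0.2 points.

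**The case for a change.** The best case for acting is that it is cheap and cannot be done later. One sentence would fix the grade before the envelope is opened, and one prespecified supportive estimate would remove a later choice about whether and how to adjust. If palpability is strongly prognostic in both arms, the gain is real. At OR 5 the half-width falls by 1.1 to 2.3 points (18.8 − 17.7 and 18.8 − 16.5). A test stratified by grade would have 87–89% power, against about 81%, at a log-odds change of 1.5 per grade.

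Part of this stands. The order of grading and opening is not stated, and a grade of uncontrolled timing should not later be used as though it were a protected baseline value. The word used is assess rather than record. But the step sits under a heading that covers intraoperative records, in a paragraph that makes a second attending physician responsible for recording parameters, and it precedes every arm-specific step.

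The rest does not amount to a fault. Nothing in the documents supports an OR of 3 or more per grade in elderly patients, or any effect in the real-time arm. With no association, the stratified test has 79% power, about 2 points less than the unadjusted test. Whether to add a supportive estimate is a matter of preference.

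**Conclusion.** The concern does not hold. Followed as written, the plan gives a valid test of first-attempt success, with no bias and no inflated type I error from leaving the grade out. An added supportive estimate would not alter the power of the primary test. It would have a half-width between 0.2 points wider (19.0 against 18.8, no association) and 0.4 points narrower (18.4 against 18.8) for odds ratios up to 2 per grade. It would gain essentially nothing up to an odds ratio of 3 if the grade matters only in the ultrasound-assisted arm.

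The validity conclusion rests on randomisation and on the grade staying out of the primary analysis. The precision figures rest on assumed grade mixes and odds ratios, because the documents give neither. Part of the SAP was not available for this review, so the statement that the grade has no analytic role covers the available text only. If the grade were used for adjustment, subgroups or a balance check, its timing relative to envelope opening would need to be known first.

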The ultrasound imaging along the longitudinal median path of the spine has less bone and ligament occlusion, and the intravertebral canal image is often clearer, which is better than the transverse or longitudinal scan of the posterior median line. Therefore, the real-time ultrasound guidance technology should adopt the paramedical approach. Chen L et al. conducted a comparison of the effects of ultrasound assisted positioning (USAS) and real-time ultrasound guidance (USRTG) in intra spinal anesthesia. In a study of 114 elderly hip fracture patients (≥ 70 years), they found that the USAS group had a higher success rate on the first attempt (successful dural puncture without redirection) (80.7% vs 52.6%) and a higher success rate on the first pass (63.2% vs 31.6%). Fewer attempts (skin piercings) (1 [1-1]vs 1 [1-3]) and median pass rates were significantly lower in the USAS group than in the USRTG group. However, the USRTG group had a shorter positioning time (175 s [129-234 s]vs 315 s [250-390 s]).

However, the operation time was longer (488 seconds [260-972 seconds]vs 200 seconds [127-328 seconds]) and the total time was longer (694 seconds [421-1133 seconds]vs 540 seconds [432-641 seconds]). The USAS group had higher satisfaction scores. Overall, anesthesiologists rated the USRTG group as "more difficult." Chen L and his colleagues believe that in elderly patients with hip fractures, USRTG technique is not superior to USAS technique for lumbar anesthesia, because USRTG technique has a lower success rate, longer operation time, lower satisfaction score, and greater difficulty in operation. Therefore, USAS technology may be more suitable for elderly patients.

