The maximum number of skin puncture should be 6 times, and the cumulative redirection of each skin puncture should not exceed 6 times. If six skin piercings are unsuccessful, traditional palpation, replacement of puncture Spaces, or general anesthesia are considered and recorded.

Whether the patient was in the left or right decubitus position, the operator used the puncture needle manually and the ultrasound probe non-manually. Adverse reactions and complications were recorded in both groups, including radicular pain, bloody cerebrospinal fluid puncture, headache after dural puncture, paresthesia, back pain, whether traditional palpation was used, the puncture space was changed, or general anesthesia was used. Patient satisfaction score: Patients were asked to use a 5-point numerical rating scale to evaluate their satisfaction (1, very dissatisfied; 5, very satisfied). The VNRS, verbal numerical rating scale (0-10) and whether to add analgesic drugs were recorded in the two groups.

3. Outcomes

Primary outcomes: first attempt success rate (first skin piercing, no redirection);

Secondary outcomes: operation time (seconds), positioning time, depth and width of posterior dural complex, skin puncture number, redirection number;

Patient satisfaction score: Patients were asked to use a 5-point numerical rating scale to evaluate their satisfaction (1, very dissatisfied; 5, very satisfied).

Operation difficulty score: After the operation, the anesthesiologist will score the difficulty of this operation (1, very dissatisfied; 5, very satisfied). Change of anesthesia method (traditional blind method, USAS or USRTG, change of puncture space, general anesthesia).

Adverse reactions and complications: include radicular pain, bleeding, puncture, headache after dural puncture, paraesthesia, and back pain.

Reference

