## Statistical analysis

All statistical analysis were performed using Statistical Package for Social Sciences (SPSS) for Windows software version 23. Numerical variables were expressed as mean  $\pm$  SD or median (minimum–maximum). Categorical variables were expressed as frequency (%). Test of normality was done using Kolmogorov–Smirnov test. One-Way analysis of variance (ANOVA) was used to compare means if data distribution was normal, or nonparametric test Mann-Whitney U was used if data was not distributed normally. Pearson chi-square or Fischer's exact test was used for assessing categorical variables. Log rank test was used to evaluate the time difference in the first administration of diclofenac sodium after surgery, and hazard ratio (HR) was used to evaluate the benefit. All tests were two-tailed, and the significance level was set at  $\alpha$  0.05.

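### The operation difficulty score carries satisfaction anchors, so as written it may record operator satisfaction under a difficulty label

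*Protocol*

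**What the plan says.** Protocol section 4, item 3 (Outcomes), lists an operation difficulty score given after the procedure: "the anesthesiologist will score the difficulty of this operation (1, very dissatisfied; 5, very satisfied". Patient satisfaction is described twice, once under item 2 (Anesthesia protocol and intraoperative records) and once under Outcomes. Both times patients are asked to "evaluate their satisfaction (1, very dissatisfied; 5, very satisfied". The two sets of anchors are the same.

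Item 2 describes the patient satisfaction score and a three-grade rating of how hard the spinous process is to palpate, but not the operator's difficulty score. It assigns patients to "either the US-AS group (n=48) or the US-RTG group (n=48", and on blinding it says: "Neither the intraoperative parameter collector nor the anesthesiologist performing the procedure can blind the groups".

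The SAP's Statistical analysis section does not name the difficulty score. It gives general rules: one-way ANOVA for normally distributed data, otherwise "nonparametric test Mann-Whitney U was used if data was not distributed normally", and for counts a Pearson chi-square or Fisher test ("exact test was used for assessing categorical variables"). All tests are two-sided.

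**The concern.** Difficulty and satisfaction are different constructs, and the Protocol's own background keeps them apart. Section 1 reports of the earlier trial in hip fracture patients that "The USAS group had higher satisfaction scores", and gives among the reasons against real-time guidance a "lower satisfaction score, and greater difficulty in operation". These are two separate findings, and they run in opposite directions. (The text does not say whose satisfaction was measured, or on what scale.)

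Two things could go wrong. An operator who follows the printed anchors would record satisfaction, and the report would call it difficulty. Or an analyst or reader, seeing only the label, could assume that a higher score means a harder procedure, when 5 is printed as the favourable end. The arm that appears easier would then be the wrong one. The score bears on a question the trial revisits, since section 1 gives greater difficulty as one reason why real-time guidance was judged not superior in the earlier trial.

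**Working it through.** The plan gives no figure for this score, so there is none to reproduce. Its only design calculation (43 per group; 43 / 0.90 = 47.8, rounded up to 48) uses first-attempt success and does not involve the score. The check is therefore a comparison of texts, followed by a short piece of algebra.

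**Step 1. The scales side by side.**

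| Item | Place in Protocol | Rater | Anchors |
|---|---|---|---|
| Patient satisfaction | Section 4, items 2 and 3 | Patient | Satisfaction, 5 favourable |
| Palpation difficulty | Section 4, item 2 | Rater not named | Difficulty, grade 1 easy to grade 3 difficult or impossible |
| Operation difficulty | Section 4, item 3 only | Anesthesiologist | Satisfaction, 5 favourable |

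The satisfaction anchors occur three times. They fit the label twice and do not fit it once. The palpation scale shows how a difficulty scale is anchored elsewhere in the Protocol, with higher meaning harder, but it is a different measurement and cannot supply the missing definition.

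**Step 2. What the text fixes and what it leaves open.** The anchors fix 5 as the favourable end. They do not settle whether the operator is rating difficulty or satisfaction. The Protocol nowhere says that a higher score means harder; that reading comes from the label alone.

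**Step 3. Would the planned tests expose a reversed reading?** Let x be a score from 1 to 5, read in reverse as 6 - x in both arms, with 48 per arm.

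- Mean difference: (6 - mean B) - (6 - mean A) = -(mean B - mean A). Same size, opposite sign.
- Mann-Whitney: U becomes 48 × 48 - U = 2304 - U. The null centre is 2304 / 2 = 1152, so the two-sided p-value is unchanged.
- ANOVA: F depends on squared deviations and is unchanged.
- Chi-square and Fisher: the score columns are only reordered, so p is unchanged.

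This would be true of any ordinal score and with any number analysed. It shows only that a reversal would go unnoticed, not that one has occurred.

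**Step 4. If readings were mixed.** Suppose a share q of ratings, at random in both arms, used the opposite direction (an assumption; the documents give no q). The expected mean is (1 - q)m + q(6 - m) = (1 - 2q)m + 6q, so the expected difference between arms is multiplied by (1 - 2q): 0.8 at q = 0.10 and 0.5 at q = 0.25. For q below one half, mixed use would shrink the expected difference without reversing it.

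**The case against.** The strongest reply is that this is a visible slip, probably carried over from the patient satisfaction line directly above, in one subjective score outside the primary outcome, and that a correct definition may stand in the part of the SAP or the record form not available here. Much of that stands. The carry-over is a plausible inference, the score is non-primary, and a correct form could exist. But recognising the slip does not reveal the intended scale: 1 could have been meant as very easy, as very difficult, or as the low end of an operator satisfaction score. If another document is right, the Protocol line still conflicts with it.

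It can also be said that the scale has a direction, because the anchors make 5 favourable. That is correct. The main open question is the construct; the wrong sign arises only for someone who reads the label and overlooks the anchors.

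A reader might infer that no test in the SAP could detect a reversal. That goes too far. The SAP also lists a log-rank test, which does not in general give the same result for x and 6 - x. It is reserved for time to first diclofenac and would not be applied here, so the statement holds for the ANOVA, Mann-Whitney, chi-square and Fisher tests only.

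**Conclusion.** The definition is wrong as written: a difficulty score has satisfaction anchors, and nothing in the text available for this review corrects it. It is a minor correction to one subjective, non-primary score, given by an operator who knows the allocation. First-attempt success, the sample size, operation time, skin punctures, redirections and the other outcomes are not touched.

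A reader might infer that the trial's difficulty result is reversed, or that its main conclusion is compromised. The documents support neither. They contain no scores and do not show how operators understood the item, so the size of any effect cannot be stated. The conclusion assumes only that the unavailable SAP text and the record form do not already settle the matter. If they do, what remains is an inconsistency between documents.

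**What to change.** In the Protocol, the record form and the SAP, replace the anchors with difficulty anchors and state the direction, for example 1 = very easy and 5 = very difficult. Either direction serves if it is stated.

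Protocol version 2.0 is dated 2024/2/1, inside the planned October 2023 to October 2024 window, so some scores may already exist; the documents do not say how many. For these, check the anchors printed on the record form before any comparison by group:

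- Difficulty was scored: keep the scores, or recode them as 6 - x if the direction was opposite to the one now stated.
- Satisfaction was scored: report them as operator satisfaction. Recoding does not turn satisfaction into difficulty.
- It cannot be determined: say so and make no directional claim about difficulty.

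The cost is about one line in each of the three documents and one check of the form. The downside is that some early scores may not be usable as difficulty. If the record form already carries difficulty anchors, only the Protocol and SAP wording needs attention.
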